9. MONITORING REPORTS

9.1. Performance Metric, SMC & DSMB Reports

This section describes the main tables and reports. A subset of these will be presented to the DSMB at each meeting. When results are presented by study arm, the arms will be labeled Arm A and Arm B. A separate document attached to the DSMB report will unblind the arms (i.e., TDF/FTC or CAB). The study accrual table will report on all enrolled women; subsequent tables will report on women who are HIV-uninfected at enrollment only.

Real-time reports will be available to the protocol team. The content of these reports will be developed by the protocol team and will generally include the following information:

- **Study Accrual**

The number of individuals enrolled and randomized per study month will be presented in a table overall and (1) by site and (2) by study arm. No formal statistical testing will be performed.

- **Baseline Demographic and Clinical Characteristics of Young women**

A table that includes baseline demographic and clinical characteristics (e.g. age, employment, marital status, education, race, BMI, HSV-2 status, etc.) will be presented. Summary statistics appropriate for the measurement scale will be used to describe the distribution of these variables. These summary statistics will be presented in tables overall, by site and by study arm. No formal statistical testing will be performed.

- **Baseline Behavioral Characteristics**

A set of tables will describe baseline behavioral characteristics for participants. Measures included in these tables will include age of sexual debut, and the number of partners in lifetime and the last 3 months, contraceptive method, and STI. Summary statistics appropriate for the measurement scale will be used to describe the distribution of these variables. These summary statistics will be presented in tables overall, by site and by study arm. No formal statistical testing will be performed.

- **Retention**

A set of tables will describe retention in follow-up for participants at each scheduled study visit. Number of women enrolled, number of women expected at each visit, number of women attending the visit early, late and on time, and percent retained will be presented. A separate retention report will be generated for women who have moved to alternative visit schedules (e.g. pregnancy, open-label TDF/FTC, annual testing); these women's visits will not be included in the standard retention table after they move to an alternative visit schedule. Retention will be presented overall and by site in the open report and by study arm in the closed report. No formal statistical testing will be performed.

- **Fidelity of Intervention**

A set of tables will describe the proportion of injections provided and the proportion of pill bottles distributed at each visit, among those retained at the visit. These tables will be presented overall and by site in the open report and by study arm in the closed report. No formal statistical testing will be performed.

- **Safety Reports (Closed Reports)**

The number and percentage of participants experiencing local reactions to the injections will be tabulated by severity and treatment arm. For a given local reaction type, each participant's

reaction will be counted once under the maximum severity for all injection visits. In addition to the individual reaction types, the maximum severity of local pain or tenderness, induration or erythema, and of systemic symptoms will be calculated. AEs will be summarized using MedDRA System Organ Class and preferred terms. Tables will show by treatment arm the number and percentage of participants experiencing an AE within a System Organ Class or within preferred term category by severity. For the calculations in these tables, a participant with multiple AEs within a category will be counted once under the maximum severity.

A listing of SAEs reported to the DAIDS Regulatory Support Center (RSC) Safety Office will provide details of the events including severity, time between onset and last dosing, and cumulative number of doses received.

Box plots of local laboratory values will be generated for baseline values and for values measured during the study by treatment arm and visit. Each box plot will show the first quartile, the median, and the third quartile. Outliers will also be plotted. If appropriate, horizontal lines representing boundaries for abnormal values will be plotted. The number (percentage) of participants with local laboratory values recorded as meeting Grade 3 AE criteria or above as specified in the DAIDS AE Grading Table will be tabulated by treatment arm. Reportable clinical laboratory abnormalities without an associated clinical diagnosis will also be included in the tabulation of AEs described above.

- **Efficacy Reports**

The efficacy reports will be shared with the DSMB committee when required as per the analysis methodology mentioned in section 7.2.2 and 7.3.1 of the SAP ()above.

9.2. Clinical Study Report

The tables described below will be included in the CSR. Additional tables and analyses may be included, at the discretion of the protocol team or sponsor, e.g., depending on the availability of additional laboratory evaluations. All reports and analyses will be presented by study arm.

Subjects will be pooled across all sites. Data will be presented by treatment group and overall. Categorical variables will be summarized by frequency distributions (number and percentages of subjects) and continuous variables will be summarized by descriptive statistics (mean, standard deviation, etc.).

Adverse events will be summarized by treatment group using the Medical Dictionary for Regulatory Activities (MedDRA) system organ class and preferred term. Tabulations will be produced for all treatment-emergent AEs (TEAEs) defined as AEs with an onset date on or after the start of treatment, treatment-related AEs (those considered by the Investigator as at least possibly drug related), SAEs, discontinuations due to AEs, and AEs by severity grade. By-subject listings will be provided for any deaths, SAEs, and AEs leading to discontinuation.

Descriptive statistics for each treatment group will be provided for clinical laboratory values (e.g., hematology, serum chemistry, and urinalysis) and vital signs data, presented as both actual values and changes from baseline relative to each on-study evaluation. Abnormal clinical laboratory values will be listed. All data will be provided in by-subject listings.

Displays of the cumulative incidence of events such as HIV infection, or treatment discontinuation, will include at-risk tables as follows: Numbers of subjects having had the event of interest, and at risk to have had the event will be shown at selected weekly timepoints under the horizontal axis. The number at risk will be computed as the number of subjects with event times greater than or equal to the given timepoint

- **Subjects Disposition**

The subject disposition summary will include the number screened, the number of screen failures, the number enrolled, the number in each patient population for analysis, the number who completed the study, the number who discontinued the study and reason for discontinuation from the study.

Disposition data will be summarized by treatment and overall. A by-subject data listing of study completion information including the reason for study discontinuation will be presented. A by-subject listing of inclusion/exclusion criteria not met will also be presented.

- **Protocol Deviations**

A summary of all protocol deviations on ITT population by type will be generated. Protocol deviation data will be summarized by treatment and overall. A by-subject data listing of protocol deviations will also be presented. All protocol deviations will be presented in a data listing.

- **Demographic and Baseline Characteristics**

Demographic and baseline characteristic data summarization will be performed to descriptively assess the comparability of treatment groups. Data to be tabulated will include age, race, ethnicity, height, weight, and BMI, as well as other baseline characteristics.

- **Exposure and Adherence**

Drug Exposure and adherence will be calculated and will be presented in a tabulation form and by listing.

- **Medical History**

A by subject listing of verbatim medical history will be presented.

- **Concomitant Medication**

Concomitant medications will be coded using the World Health Organization (WHO) dictionary. Results will be tabulated by anatomic therapeutic class (ATC) and preferred term. This data will be summarized by treatment group. Previous and concomitant medications will be presented in a data listing.

- **Vital Signs and Physical Examination**

Vital sign measurements will be presented for each subject in a data listing. Systolic blood pressure, diastolic blood pressure, heart rate, and weight will be summarized as actual value and change from baseline by visit. All physical examination findings will be presented in a data listing.

- **Laboratory Data**

Clinical laboratory values will generally be expressed in SI units .

The actual value and change from screening will be summarized for each clinical chemistry, hematology, lipid panel, HbA1C and urinalysis parameters and by each visit. In the event of repeat values, the last non-missing value per visit will be used.

All laboratory data will be also provided in data listings. Values outside of the lab parameter's normal range will be flagged as high, low, or abnormal based on the range of the test.

Laboratory results will be summarized by scheduled study visit. Summary calculations such as maximum post-baseline level will include data from interim (unscheduled visits). Formal comparisons of laboratory findings between arms will not be included in the CSR.

- **Adverse Events**

The reporting of safety data is descriptive and will include all subjects who receive at least one dose of investigational product. AEs will be summarized based on the frequency of AEs and their severity for all treated subjects. All AEs will be coded using Medical Dictionary for Regulatory Activities (MedDRA) and summarized by treatment group. Data will be summarized using preferred term and primary system organ class.

If a subject experiences multiple events that map to a single preferred term, the greatest severity will be assigned to the preferred term for the appropriate summaries.

Summaries of AEs will include any AEs reported beginning with the first dose of investigational product on Day 1. The occurrence of adverse events will be summarized by treatment group using preferred terms, system organ classifications, and severity. Separate summaries of serious adverse events, adverse events related to investigational product, and events leading to the discontinuation of investigational product will be generated. All adverse events reported will be listed for individual subjects showing both verbatim and preferred terms.

- **Efficacy and Efficacy Subgroups**

In the Clinical Study Report, primary efficacy analysis will be presented as described in Section 7.3.1. For subgroup analyses, the age and BMI subgroup analyses will be presented in the Clinical Study Report, but analyses considering contraceptive use and HSV-2 status at baseline will not be presented in the Clinical Study Report.

10. Summary of changes

10.1 Version 3.0 was prepared during the planning process for the Clinical Study Report. The blinded statistician continued to not have access to individual level data.

10.1.1. Analysis Populations

- Populations were adjusted, renamed, or clarified: mITT; Per Protocol; Seroconverter; Contraceptive Substudy; Pregnancy.
- Populations were added: Randomized; ITT; Primary Safety; Step 2 Safety; Step 2 Efficacy; Longitudinal Pharmacokinetic Cabotegravir; TDF/FTC Adherence Population; Confirmed Pregnancy; Seroconverter Population; Primary Seroconverters; Declined Contraception; Infected at Enrollment
- The Version 2.0 “Per-Protocol” analysis dataset was redefined and renamed as On Blinded Study Product (OBSP) censoring. The new “Per-Protocol” population was

defined as being based upon deviation adjudication. The adjudication process was described.

- The age and BMI subgroups were modified with adjusted cut-points.

10.1.2. *Analysis Details and Clarifications*

- Clarifications and additional details were added throughout the Statistical Analysis section.
- A section was added to describe missing data handling and imputations.
- Appendices were added to provide detail for visit windowing, efficacy and safety analysis censoring details and OBSP specifications, a listing of study sites, a listing of adverse events of special interest (AESI). Key variable definitions, which were based on data fields found in the CRF data, were removed.

10.1.3. *Reports*

- A new section was added to describe the contents of the following reports: Performance metrics, SMC, DSMB, and CSR.

10.2 Version 4.0 (current version) contains corrections and additional details requested for Clinical Study Report programming. The blinded statistician continued to not have access to individual level data during these revisions.

10.2.1. *Adverse Events of Special Interest*

- The appendix describing AESI was inadvertently truncated in Version 3.0. This has been corrected.

10.2.2. *Censoring details for Time to Treatment Discontinuation due to Safety*

- Definitions for events, competing events, and censored observations were added as Appendix

10.2.3. *Description of the per-protocol efficacy analysis*

- Censoring definition for per-protocol partial exclusions was added to Section 7.3.1

10.2.4. *Revision to the date imputation algorithm for Concomitant and Prior Medications*

- A modification was made to section 8.1 to account for the fact that prior medications would have a start date prior to the randomization date.

10.2.5. *Description of the per-protocol efficacy analysis*

- Censoring definition for per-protocol partial exclusions was added to Section 7.3.1

10.2.6. *Clarification of the Injection (Step 2) Efficacy Population*

- A modification was made to section 6.5 to state that a participant had to have at least one follow-up visit with HIV status evaluated to be included in this population.

10.2.7. *Clarification of Confirmed Pregnancy Population*

- Clarification added to Section 6.12 to define additional ways that a pregnancy can be confirmed.

10.2.8. *Subgroup definitions*

- Section 6.17 was revised. Formerly, the age subgroups were defined as:

“Age: ≤ 24 vs > 24 years old.” This was rewritten as:

“Age:<25 vs ≥ 25 years old.”)This would not affect the classification of subjects into age categories.)

- The contraception subgroups were clarified to indicate reference to method during follow-up. Details of efficacy analyses involving this time-dependent covariate were added to Section 7. 3.6.
- A note was added to indicate that HSV-2 status at baseline will not be available for the Clinical Study Report. This note is repeated in Section 9.2.

APPENDIX A - Study Visit Windows

HPTN 084 Visit Codes, Target Days, and Visit Windows

HPTN 084 Visit Codes, Target Days, and Visit Windows

Week	Visit Code	Day allowable window opens	Day target window opens	Target Day	Day target window closes	Day allowable window closes
Screening	1.0	--	--	--	--	--
Step 1						
Day 0/Enrollment	2.0	0	0	0	3	6
Week 2	3.0	7	11	14	17	20
Week 4*	4.0	21	25	28	31	31
Step 2*						
Day 0/Week 5*	5.0	0	0	0	3	3
Week 6	6.0	4	4	7	10	17
Week 9	7.0	18	25	28	31	41
Week 13	8.0	42	53	56	59	69
Week 17	9.0	70	81	84	87	97
Week 21	10.0	98	109	112	115	125
Week 25	11.0	126	137	140	143	168
Week 33	12.0	169	189	196	203	224
Week 41	13.0	225	245	252	255	255
Week 42	14.0	256	256	259	266	283
Week 49	15.0	284	301	308	315	336
Week 57	16.0	337	357	364	371	392
Week 65	17.0	393	413	420	427	448
Week 73	18.0	449	469	476	483	504
Week 81	19.0	505	525	532	539	560
Week 89	20.0	561	581	588	595	616
Week 97	21.0	617	637	644	651	672
Week 105	22.0	673	693	700	707	728
Week 113	23.0	729	749	756	763	784
Week 121	24.0	785	805	812	819	840
Week 129	25.0	841	861	868	875	896
Week 137	26.0	897	917	924	931	952
Week 145	27.0	953	973	980	987	1008
Week 153	28.0	1009	1029	1036	1043	1064
Week 161	29.0	1065	1085	1092	1099	1120
Week 169	30.0	1121	1141	1148	1155	1176
Week 177	31.0	1177	1197	1204	1211	1232
Week 185	32.0	1233	1253	1260	1267	1288

Week	Visit Code	Day allowable window opens	Day target window opens	Target Day	Day target window closes	Day allowable window closes
Step 3**						
Day 0 (Step 3 only)	33.0	0	0	<8 weeks from last injection	14	42
Week 12	34.0	43	70	84	98	126
Week 24	35.0	127	154	168	182	210
Week 36	36.0	211	238	252	266	294
Week 48	37.0	295	322	336	350	378

*Please note that the Week 4 and Week 5 Visits must be completed in order for a participant to move to Step 2. If a Week 4 or Week 5 Visit is delayed or missed, contact the CMC for further guidance.

**The target dates for all Step 2 visits are based off of the actual date of the Week 5 Visit. The target dates for all Step 3 visits are based off of the first Step 3 Visit, called “Step 3/Day 0”.

Open Label Truvada Schedule						
Week	Visit Code	Day allowable window opens	Day target window opens	Target Day	Day target window closes	Day allowable window closes
Day 0 (date injections permanently discontinue)	V201/or other*	0	0	0	14	42
Week 12	202.0	43	70	84	98	126
Week 24	203.0	127	154	168	182	210
Week 36	204.0	211	238	252	266	294
Week 48	205.0	295	322	336	350	378

- Day 0 for Open Label Truvada Schedule may be a Step 2 visit code or 201. See Section 13.5 Alternate Visits.

Pregnancy Schedule*						
Week	Visit Code	Day allowable window opens	Day target window opens	Target Day	Day target window closes	Day allowable window closes
Day 0 (First positive Pregnancy Test)	XX.X	0	0	0	0	0
4 weeks after first positive pregnancy test	Interim visit XX.X	21	--	28	--	35

Quarterly Visit 1 (12 weeks since first positive pregnancy test)	101	43	70	84	98	126
Quarterly Visit 2 (24 weeks since first positive pregnancy test)	102	127	154	168	182	210
Quarterly Visit 3 (36 weeks since first positive pregnancy test)	103	211	238	252	266	294

*Pregnancy schedule is to be followed throughout pregnancy and while participant is breastfeeding.

Yearly/Annual Visits						
Week	Visit Code	Day allowable window opens	Day target window opens	Target Day	Day target window closes	Day allowable window closes
Day 0 (Last visit participant at clinic HIV Test conducted)	XX.X	0	0	0	0	0
Yearly Visit 1	50.0	182	358	365	372	548
Yearly Visit 2	51.0	547	723	730	737	913
Yearly Visit 3	52.0	912	1088	1095	1102	1278
Yearly Visit 4	53.0	1277	1453	1460	1467	1643
Yearly Visit 5	54.0	1642	1818	1825	1832	2008

Seroconverter Schedule						
Week	Visit Code*	Day allowable window opens	Day target window opens	Target Day	Day target window closes	Day allowable window closes
HIV Confirmatory Visit	XX.X	0	0	0	14	42
Week 12	XX.X	43	70	84	98	126
Week 24	XX.X	127	154	168	182	210
Week 36	XX.X	211	238	252	266	294
Week 48	XX.X	295	322	336	350	378

*Due to unblinding considerations, there are no unique visit codes for seroconverters. The visit codes should reflect the next study visits for the participants.

APPENDIX B - Details of Efficacy Analysis Definitions

Population Definition:

Modified ITT

- Participant is randomized
- Participant is HIV uninfected at randomization (determined by EAC)
- Participant does not have a major enrollment violation – determined by independent adjudication

Note: Only participants with at least one follow-up visit (of any type, including safety and interim visits) with HIV status determined after enrollment will contribute study time to the efficacy analysis.

Censoring for primary efficacy analysis:

- If a study-wide transition to Step 3 occurred, all data from the enrollment visit through the date of transition (plus one month?) will be included
- If no study-wide transition to Step 3 occurred or if the study is stopped early, all ongoing follow-up at the time of decision to stop the blinded portion of the study will be censored on the date of study closure.

Censoring for on blinded study product (OBSP) analysis

Participants will be censored when an injection is delayed, defined as follows:

- **Last non-delayed injection:** The earliest of an injection whose subsequent injection is delayed for the first time (i.e. given >6 weeks after the Week 5 injection or >10 weeks after any other injection) or the last injection before a termination or a permanent product discontinuation
- Follow-up time will be censored at the last visit with HIV status determined up through 6 weeks after the Week 5 injection, if that is the last non-delayed injection, or 10 weeks after the last non-delayed injection for subsequent injections.

Calculation of study time for primary efficacy analysis:

- If HIV infected, study time will be calculated as the number of days between enrollment and the mid-point between first visit where HIV infection was detected and the most recent prior visit where HIV infection was not detectable, as determined by the EAC.
- If HIV uninfected, study time will be calculated as the number of days between enrollment and the last visit with HIV status at or before the censoring time.

Calculation of study time for OBSP analysis:

- If HIV infected prior to OBSP censoring, study time will be calculated as the number of days between enrollment and the mid-point between first visit where HIV infection was detected and the most recent prior visit where HIV infection was not detectable, as determined by the EAC.
- If HIV uninfected At OBSP censoring time, study time will be calculated as the number of days between enrollment and the last visit with HIV status at or before the OBSP censoring time.

Primary endpoint:

- Only infections that are confirmed by the EAC and detected within the analysis timeframe at the time of the final primary analysis adjudication (date of first positive visit as determined by the EAC within the analysis timeframe) will be considered. Infections that are not confirmed by the EAC or that occur out of the analysis timeframe will not be included as primary endpoints.

Interim Analysis (mITT and OBSP) specification

Interim analysis procedures will follow the primary analysis definitions above with the exception that the analysis timeframe will be truncated at the interim-analysis data cut date, as follows.

mITT analysis

- All data from enrollment through the interim analysis cut date will be considered

OBSP analysis

- If there is an injection delay prior to the data cut, all data up to the last visit with HIV status determined that occurred prior to the data cut date and within 6/10 weeks for the first/subsequent injection of the last non-delayed injection will be considered.
- If there is no injection delay prior to the data cut point, data included as for the ITT analysis

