2.7.4. Pregnancy

A participant with a first positive pregnancy test will temporarily discontinue blinded injections and receive a 4-week supply of open label TDF/FTC and may resume blinded treatment if a second test after 4 weeks indicates that she is not pregnant. All pregnant participants with a confirmed positive pregnancy test (four weeks after the initial pregnancy test) will be unblinded and followed by the study every 12 weeks. Regardless of the randomization assignment or point in the study, all pregnant participants will be placed on open-label TDF/FTC for the duration of the pregnancy. Once pregnancy outcome is reached, and after the participant is not breastfeeding, she may resume study product, according to original randomized arm but open-label, and resume visits per the study schedule.

If participants decline to use an approved contraceptive method, they will be given open-label TDF/FTC for 48 weeks starting no later than eight weeks after her last CAB LA/placebo injection. If study follow-up is ongoing she will be required to be followed up at least annually for HIV testing thereafter. If a participant transitioned to open-label TDF/FTC during Step 2, either because she wanted to become pregnant or declined to continue using long-acting contraception, and subsequently changes her mind she may continue in the study on blinded study product (per original randomization) once she has documentation of a negative pregnancy test and of resuming long-acting contraception.

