4.3 Blinding

Study site staff, except for the site Pharmacist of Record or their designee, and participants will be blinded to the random assignments. Blinding will be maintained until the trial is completed or stopped, i.e., the trial is stopped early, or the required number of endpoints (114) has been met. At a specified time directed by the HPTN Statistics and Data Management Center, participants will be notified of their treatment assignment.

In addition, as described in sections 5.14 and 5.18 of the HPTN Protocol 084, v2.0, participants with a confirmed pregnancy will be unblinded. Participants who are unblinded due to pregnancy may restart open-label study product in their original randomization arm (open label CAB LA or TDF/FTC) following delivery and cessation of breastfeeding.

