
Ho: HR = 1

Ha: HR < 1

A two-sided test with $\alpha = .05$ will be used. The estimated hazard ratio (HR), a 95% confidence interval, and a p-value for the hypothesis shown above will be given. If the number of events is small (<40) then the p-value will be confirmed using a permutation test based on 100,000 random permutations of the treatment assignments; if there is a meaningful difference between the permutation and asymptotic procedures, the permutation p-value will be used. Treatment efficacy will be estimated as $TE = 1 - HR$.

If the trial is stopped early (prior to the final analysis), then the primary results will be reported as a bias-adjusted mean HR and design-adjusted 95% CI (Emerson S and Fleming TR. Symmetric Group Sequential Test Designs. *Biometrics* 45:904-923, 1989).

7.3.1.1. Sensitivity of the Primary mITT results:

The following sensitivity analyses are proposed to aid in interpretation of the primary ITT results :

- A per-protocol analysis, excluding participants with exclusionary protocol violations, will be conducted if the number of participants affected exceeds 2% of the enrolled population.
Population: Per Protocol
This analysis will be identical to the mITT analysis, except that for partial exclusions, the follow-up will be censored on the last non-missing HIV test result date on or prior to the date of the deviation that resulted in exclusion from the per-protocol population.
- A supportive analysis will be presented using the OBSP censoring in the Injection (Step 2) Efficacy population (see OBSP censoring definitions in appendix B), where study follow-up is censored when a participant does not receive blinded injection study product on time.
- In this active control trial, the superiority of CAB LA is predicated in part on incomplete adherence to daily oral TDF/FTC. Specifically, we assume that overall adherence to TDF/FTC will be less than 50%. If adherence to TDF/FTC is high (greater than 50%) then, as described in section 7.8.4 of the protocol, a supportive non-inferiority (NI) analysis of CAB LA versus TDF/FTC may provide valuable information for interpreting the trial results.

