7.3.2. Primary Safety Analysis

Objective: To evaluate the relative safety of oral CAB/CAB LA (oral run-in and injections, Steps 1 and 2) vs. daily oral TDF/FTC for HIV prevention (Steps 1 and 2).

Population: Safety population

The primary pre-specified safety comparison between arms will be based on all AEs with maximum grade ≥ 2 . In general, formal statistical comparison of individual types of safety events across arms is not planned since interpretation of differences must rely heavily upon clinical judgment. Where formal statistical testing is considered necessary to guide judgement of observed differences for any single event or collection of events, differences in events grade 2 and higher will be assessed. The event rate and 95% robust confidence interval for each treatment arm will be calculated using a log-linear model for counts using log(person-time) as an offset, treatment as a covariate, assuming a Poisson distribution and using a robust variance (i.e. generalized estimating equations). Event rates will be compared between treatment arms using this same model. Event rates will be compared between treatment arms using this same model and a type I error rate of $\alpha=0.05$ is prespecified. Very rare events will be compared using an exact Poisson test. Additional supporting descriptive safety analyses will be presented.

For Safety OBSP analysis, adverse event follow-up will be censored after the last injection before a termination or a permanent product discontinuation regardless of any delays in injections. If termination or a permanent product discontinuation occurs prior to their first injection, the participant's follow-up time will be censored at the termination or permanent product discontinuation date +1. If termination or a permanent product discontinuation occurs after the first injection, the participants follow-up time will be censored up through 6 weeks after the Week 5 injection, if that is the last injection, or 10 weeks after the last injection for subsequent injections.

7.3.3. Adverse events in Step 1

Objective: To compare the safety of oral CAB vs. oral TDF/FTC in Step 1

Population: Primary Safety

Censoring: AEs are censored at 120 days after randomization for participants who never received an injection; at 1 day after the date of termination or investigational product discontinuation; at date of first injection, whichever occurs first. Reported AEs will be excluded if they occur after the censoring time.

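### On-blinded-product (OBSP) censoring misses women whose injections lapse with no later injection and no permanent stop recorded, and its interim and safety versions do not agree with Appendix B

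*SAP*

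**What the plan says.** **Intent.** Section 7.3.1.1 presents OBSP as a supportive efficacy analysis in the Injection (Step 2) Efficacy Population, "where study follow-up is censored when a participant does not receive blinded injection study product on time".

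**Final efficacy rule (Appendix B).** Follow-up ends at the last visit with known HIV status within 6 weeks of the Week 5 injection, or within 10 weeks of a later one, counted from the last non-delayed injection. That injection is defined by two triggers:
- "The earliest of an injection whose subsequent injection is delayed for the first time", where delayed means "given >6 weeks after the Week 5 injection or >10 weeks after any other injection";
- in the alternative, the final injection that a woman had before she left the study or stopped product for good.

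**Interim rule (Appendix B).** The lead-in says that interim procedures follow the definitions above, truncated at the data cut. The second OBSP bullet then reads: "If there is no injection delay prior to the data cut point, data included as for the ITT analysis".

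**Safety.** Section 7.3.2 states that "adverse event follow-up will be censored after the last injection before a termination or a permanent product discontinuation regardless of any delays in injections". Section 7.3.4 (Step 2 adverse events, OBSP) refers the reader to Appendix B for the censoring definitions.

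**How a woman can be off blinded product without a permanent stop.** Under section 2.7.4 a first positive pregnancy test leads to a temporary halt of injections. Once pregnancy is confirmed, "all pregnant participants will be placed on open-label TDF/FTC for the duration of the pregnancy". After delivery and breastfeeding she may restart her randomized product open-label. Section 4.3 adds that "participants with a confirmed pregnancy will be unblinded". Section 7.3.1 keeps open-label time in the primary analysis, in the randomized arm.

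**The concern.** The stated intent turns on an injection not being received on time. The operating delay trigger turns on a later injection having been given late. The two differ for a woman who has had no later injection by the cut-off. If no termination or permanent discontinuation is recorded for her either, nothing ends her OBSP follow-up, and open-label TDF/FTC time is analysed as time on blinded product.

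The gap matters more at an interim cut, when paused women are less likely to have had a next injection. There the second bullet also leaves out termination and permanent discontinuation. For safety, two sections use the same OBSP label for different rules. Under section 7.3.2, open-label time during a pause and after an open-label restart can be counted as on blinded product.

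At stake is the meaning of the OBSP estimates: followed literally, they would not be the on-blinded-product effect that the SAP says they are.

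**Working it through.** **Step 1: apply the wording to each way of being off blinded product.**

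1. *Permanent stop or termination, final efficacy analysis.* The second trigger fires, and time ends 6/10 weeks after the last injection. Censored as intended.
2. *Permanent stop or termination before an interim cut, no late injection.* The second interim bullet read alone gives ITT data. The lead-in, with both triggers placed under the delay definition, gives censoring. The text conflicts.
3. *Pause or missed injection, later injection given beyond 6/10 weeks.* The first trigger fires. Censored.
4. *Pause or missed injection, no later injection by the cut-off, no permanent stop recorded.* Neither trigger fires in the final rule, and the interim bullet gives ITT data. Not censored, contrary to section 7.3.1.1.
5. *Safety OBSP, pause with or without an open-label restart.* Section 7.3.2 ignores the delay and time continues. Under Appendix B, to which section 7.3.4 points, a late restart does trigger censoring. The two rules differ.

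State 4 can arise from the trial's own procedures. Appendix A gives pregnancy its own visit schedule, separate from the open-label schedule, whose day 0 is the date of permanent discontinuation. Appendix C lists a positive pregnancy test among reasons for treatment discontinuation without saying whether it is permanent. Two programmers could therefore classify the same woman differently.

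**Step 2: reproduce the plan's rates.** By the formula under Table 4.1:
- CAB: 3.5 × (.15 × .80 + .20) = 1.12 per 100 person-years.
- TDF/FTC: 3.5 × (.15 × .48 + .52) = 2.07.
- Ratio: 1.12/2.07 = .541, against .54 in the SAP.

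**Step 3: illustrate the effect on the OBSP hazard ratio.** The SAP gives no rate of pauses and no open-label person-time. Assume a share f of OBSP person-time is really open-label TDF/FTC with incidence r.

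Both arms affected: HR = [(1−f) × 1.12 + f × r] / [(1−f) × 2.07 + f × r]

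CAB arm only: HR = [(1−f) × 1.12 + f × r] / 2.07

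Full open-label adherence means r = 3.5 × (1 − .85) = .525.

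| Scenario | f = 2% | f = 5% | f = 10% |
|---|---|---|---|
| Both arms, r = 2.07 | .550 | .564 | .587 |
| Both arms, r = .525 | .543 | .547 | .554 |
| CAB arm only, r = .525 | .535 | .527 | .512 |

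Example, first row, f = 5%: (.95 × 1.12 + .05 × 2.07)/2.07 = 1.1675/2.07 = .564. In that row the TDF/FTC arm's rate is unchanged, so the whole shift comes from CAB-arm time.

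**The case against.** The strongest reply is that the rules already do most of the job:

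- Appendix B removes permanent stoppers from the final efficacy analysis without needing a later injection. This stands. A reader might infer that OBSP fails to remove women who stopped blinded product in general; the second trigger contradicts that.
- The interim lead-in imports the definitions above, and Appendix B puts permanent discontinuation under the delay definition. That is a fair reading, but the bullet that follows states a different result in plain terms. The interim point is therefore a conflict to remove, not a proven omission.
- Confirmed pregnancy brings unblinding and only an open-label restart, so it may be recorded as a permanent end of blinded product. If so, the second trigger fires. The SAP does not say, and section 2.7.4 also lets some women who moved to open-label product for contraceptive reasons return to blinded product.
- Ignoring delays in Safety OBSP is an explicit choice. This stands as to delays. It does not explain counting open-label time as blinded, nor the referral to Appendix B in section 7.3.4.

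A reader might also infer that the error must dilute the contrast. It need not: in the TDF/FTC arm the drug is the same, and the direction depends on which arm is affected and on open-label adherence. Nor can the size be had by assuming 2-8 stops or pauses per 100 person-years. That gives 2.6%-10% of person-time only by pooling permanent stops with pauses and letting no one return.

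**Conclusion.** The concern holds in a limited form. For women whose injections are paused or missed, with no later injection and no permanent stop recorded, the efficacy OBSP rule does not do what section 7.3.1.1 says. The interim bullet conflicts with its own lead-in over permanent stoppers, and the safety versions of OBSP disagree.

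The size is unknown. The hazard ratios above, .512 to .587 against .541, rest on an assumed 2-10% of misclassified person-time and on assumed open-label incidence. They show that the estimate could move either way, not by how much it will. No safety rate ratio can be derived from the SAP.

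OBSP is supportive. The primary mITT test and the 114-event design are unaffected. The correction should still be made, because it is cheap and the present text can be programmed in more than one way.

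**What to change.** These changes concern analysis censoring only.

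1. **Appendix B, final rule.** Define a delay as no blinded injection received by 6 weeks after the Week 5 injection, or by 10 weeks after any later one, whether or not a later injection is ever given. Keep termination and permanent discontinuation as the second trigger.
2. **Appendix B, interim rule.** Replace the second OBSP bullet with: *if there is no injection delay, termination or permanent product discontinuation before the data cut, data are included as for the mITT analysis.*
3. **Sections 7.3.2 and 7.3.4.** Reconcile the two safety rules. Safety OBSP may keep its tolerance of delays, but its time should end at unblinding or the move to open-label product after a confirmed pregnancy. It should not end at the temporary 4-week supply when the woman then resumes blinded product.

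The cost is a SAP wording change, a small change to the censoring derivation, and slightly less OBSP person-time.
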